## 3. STUDY DESIGN

## **3.1. GENERAL DESCRIPTION**

This is a Phase 3, randomized, double-blind, placebo-controlled, in-patient, safety, and efficacy study to evaluate HP-3070 for the treatment of schizophrenia.

This study will consist of a Screening/placebo Run-in Period of 3 to 14 days, a 6-week double-blind Treatment Period and a 30 day Follow-up Period.

Subjects will be hospitalized at the Screening Visit and will remain hospitalized during the study. The subject may leave the hospital study for necessary personal business. Any subject who leaves the site must have an alcohol breathalyzer and urine drug tests when they return to the site.

After obtaining informed consent, each subject will be assigned a unique subject number. Eligible subjects will be hospitalized for the duration of the study. While undergoing screening procedures and waiting for results of laboratory tests, ECGs, and other assessments, the subject will start treatment with the single-blind placebo patch. The subject must have the single-blind placebo patch applied for a minimum of 3 days prior to being randomized into the double-blind Treatment Period. In addition, current antipsychotic and other prohibited medications will be washed out during the run-in period and must be completed prior to randomization into the double-blind treatment period. Details in regard to wash-out periods for specific drugs are summarized in Protocol Section 5.10.1. Subjects who have a decrease in PANSS total score ≥20% from Screening to Baseline or a PANSS total score <80 at Screening or Baseline will be discontinued from the study and will not enter the double-blind Treatment Period.

Document:	\\quintiles.net\Enterprise\Apps\sasdata\SASb\SAS\Noven\HP-			
Documenti	3070\XWA17541\Biostatistics\Docu	imentation\SAP\Final 6\Noven HP-3070-GL-04 S/	AP text Final	
	6_18Jan2018.docx			
Author:	[name]	Version Number:	Final 6	
		Version Date:	18Jan2018	
Template No:	CS TP BS016 – Revision 3	Reference: C	CS WI BS005	

Effective Date: 01May2012

Copyright © 2012 Quintiles Transnational Corp. All rights reserved.

Noven Pharmaceuticals, Inc. STATISTICAL ANALYSIS PLAN: PROTOCOL HP-3070-GL-04 Page 12 of 50

Subjects eligible for randomization into the double-blind Treatment Period will be randomly assigned to HP-3070 9.0 mg, HP-3070 18.0 mg, or placebo in a 1:1:1 ratio stratified by country. Subjects will receive treatment with study medication daily for 6 weeks.

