The study will evaluate 9.0mg (HP-3070 9.0 mg) and 18.0 mg (HP-3070 18.0 mg) of HP-3070 transdermal patches versus placebo transdermal patches. Patches will be applied by site personnel at approximately the same time daily and each patch will be worn for 24 hours. Every day, 24 hours (±15 minutes) after patch application, site personnel will remove previous day's patches and apply new patches.

All subjects will have a follow-up contact (site visit or telephone call, at the discretion of the Investigator) 30 days after the last patch is removed. This contact will be used to collect information about any Adverse Events (AEs) or Serious Adverse Events (SAEs) that may have occurred since discharge and to follow-up on any Adverse Events (AEs) that were on-going at discharge.

Assuming an effect size of 0.35 on the change in PANSS total score from baseline to Week 6 for the two pairwise comparisons between each active HP-3070 treatment arm and placebo, the power for detecting a statistically significant HP-3070 advantage will be approximately 0.90 having 204 evaluable subjects per each treatment arm, using a two-sided alpha level of 0.025 for each comparison. A two-sided overall type I error is equal to 0.05. Having three treatment arms, the total number of subjects randomized in the trial and included in primary analysis set will be approximately 612.

The effect size of 0.35 (difference between means equal to 7 and common standard deviation (SD) equal to 20) was chosen based on the lowest effect size observed in results from the studies conducted with sublingual (SL) asenapine and approved by the Food and Drug Administration (FDA) (Sycrest®/SAPHRIS® [Study 041004, and Study 041023]).

A sample size recalculation (SSR) will be conducted as described in Section 4.2 on the blinded data after approximately 50% of the originally planned number of subjects have been randomized and completed up to 6 weeks of study treatment.

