Copyright © 2012 Quintiles Transnational Corp. All rights reserved.

Effective Date: 01May2012

Noven Pharmaceuticals, Inc. STATISTICAL ANALYSIS PLAN: PROTOCOL HP-3070-GL-04 Page 27 of 50

in PANSS total score as the repeated dependent variable, with country, treatment (HP-3070 9 mg, HP-3070 18 mg, and placebo), visit (Weeks 1, 2, 3, 4, 5, and 6), treatment by visit interaction, and the Baseline PANSS total score as covariates. An unstructured covariance matrix will be assumed. In the event the convergence cannot be attained with the unstructured correlation matrix, the following alternative structures will be attempted in the specified order (from least restrictive to most restrictive): heterogeneous Toeplitz structure (TOEPH), heterogeneous autoregressive(1) (ARH(1)), heterogeneous compound symmetry (CSH), No Diagonal Factor Analytic (FA0(q), with q equal to the number of time points), Toeplitz structure (TOEP), autoregressive(1) (AR(1)), and compound symmetry (CS). The first structure in this list with which the model converges will be used. If either ARH(1) or AR(1) structure is used, a random subject intercept will also be included in the model. The Restricted Maximum Likelihood (REML) method will be used for the estimation of the covariance parameters. The Kenward-Rogers method will be used to estimate the denominator degrees of freedom. The treatment-by-time interaction term allows for comparisons of the treatment groups at each time point. Treatment comparisons of each HP-3070 dose to placebo at Week 6 will be used for the primary analysis.

SAS procedure MIXED will be used to perform this analysis as follows:

proc mixed data=<analysis dataset>;

class TRT COUNTRY VISIT SUBJID; model CHG = TRT COUNTRY VISIT TRT\*VISIT BASE / ddfm=kr; repeated VISIT / type=un subject=SUBJID; Ismeans TRT\*VISIT / cl pdiff=all;

run;

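### SAP Section 15.1.3 lists FA0(6), the unstructured matrix in Cholesky form, fourth among fallbacks said to run from least to most restrictive, so a failed UN fit drops to TOEPH first

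*SAP*

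**What the plan says.** Section 15.1.3 fits the primary MMRM to change in PANSS total score with repeated factor "visit (Weeks 1, 2, 3, 4, 5, and 6", baseline as a covariate, and an unstructured covariance matrix. If that does not converge, "the following alternative structures will be attempted in the specified order (from least restrictive to most restrictive". The order is TOEPH, ARH(1), CSH, then "No Diagonal Factor Analytic (FA0(q), with q equal to the number of time points", then TOEP, AR(1) and CS. The first structure that converges is used, with no fit criterion to choose among them. If ARH(1) or AR(1) is used, a random subject intercept is added.

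Estimation is by REML with Kenward-Roger degrees of freedom. The PROC MIXED code in the section requests no empirical (sandwich) variance. Section 15.2.3 applies the same method to CGI-S, and Section 15.3.3.1 applies it to the other continuous endpoints. The Week 6 p-values for PANSS and CGI-S enter the gatekeeping procedure of Section 7.4.

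**The concern.** The list states a principle and one entry violates it. FA0(q) with q equal to the number of repeated time points is not an intermediate structure. It is the unstructured matrix in another parameterisation, so on the stated principle it belongs immediately after UN. Under the first-to-converge rule its place in the list decides the model: FA0(6) is reached only if TOEPH, ARH(1) and CSH have all failed as well.

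What is at stake is the standard error of the Week 6 contrasts. A UN failure would replace the planned unrestricted covariance with one that forces equal correlations at equal lags, while an unrestricted form was still untried. With model-based errors, a wrong structure passes straight into the confirmatory p-values and confidence intervals.

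**Working it through.** **Inputs from the SAP.** Section 3.1: "difference between means equal to 7 and common standard deviation (SD) equal to 20", "having 204 evaluable subjects per each treatment arm", "using a two-sided alpha level of 0.025 for each comparison". Section 15.1.3: six post-baseline visits, with baseline a covariate and not a repeated measure, so t = q = 6.

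**The plan's own figure.** The SAP gives no number for the fallback rule, but its sample size reproduces. The normal approximation is n = 2·20²·(2.2414 + 1.2816)²/7² = 202.6, that is 203 per arm. The exact two-sided t-test at 0.025 needs 204, with power 0.9002, as stated.

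**Parameter counts at t = 6.**

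| Order in SAP | Structure | Formula | Parameters |
|---|---|---|---|
| planned | UN | t(t+1)/2 = 6·7/2 | 21 |
| 1 | TOEPH | 2t−1 | 11 |
| 2 | ARH(1) | t+1 | 7 (8 with the added intercept) |
| 3 | CSH | t+1 | 7 |
| 4 | FA0(6) | q(2t−q+1)/2 = 6·7/2 | 21 |
| 5 | TOEP | t | 6 |
| 6 | AR(1) | 2 | 2 (before the added intercept) |
| 7 | CS | 2 | 2 |

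FA0(6) is LL′ with L a full 6×6 lower triangle. Every positive definite 6×6 matrix has such a factorisation, so FA0(6) spans the UN model, restricted only to be nonnegative definite. It is the least restrictive entry on the list.

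**Consequence of landing on TOEPH.** The SAP states no correlations or dropout rate, so these are assumptions:
- SDs rise linearly from 11 at Week 1 to 20 at Week 6.
- Adjacent-visit correlations change linearly, and the correlation between more distant visits is the product of the adjacent ones between them.
- Dropout is monotone and spread evenly over the visits, with 20% or 30% missing at Week 6.

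TOEPH is fitted by expected likelihood. The ratio r is its model-based Week 6 SE divided by the true SE of the same estimator. A nominal two-sided test at α then runs at 2Φ(−z·r), where z is the 1−α/2 normal quantile. Ranges cover 20% and 30% dropout.

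| Adjacent correlations | r | Actual level, nominal 0.05 | Actual level, nominal 0.025 |
|---|---|---|---|
| constant (Toeplitz) | 1.000 | 0.050 | 0.025 |
| rising 0.80 to 0.88 | 0.950-0.952 | 0.062-0.063 | 0.033 |
| rising 0.75 to 0.90 | 0.915-0.918 | 0.072-0.073 | 0.040 |
| rising 0.70 to 0.95 | 0.859-0.863 | 0.091-0.092 | 0.053-0.054 |
| falling 0.88 to 0.80 | 1.05-1.06 | 0.038-0.039 | 0.018 |
| falling 0.90 to 0.75 | 1.10 | 0.030-0.031 | 0.013-0.014 |
| falling 0.95 to 0.70 | 1.20-1.21 | 0.018-0.019 | 0.007 |

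The 0.025 column is relevant because the truncated Hochberg step in Appendix 2 compares the smaller primary p-value with 0.05/2 = 0.025. The larger is compared with (0.9 + 0.1/2)·0.05 = 0.0475.

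**Finite-sample check.** REML fits of TOEPH to simulated trials of 3 × 204 subjects with no treatment effect used steeper patterns, SDs of 10 to 20 and 22% missing at Week 6. Correlations rising 0.55 to 0.92 gave r = 0.852 and rejection of 0.051 at nominal 0.025 (185 replicates). Correlations falling 0.92 to 0.55 gave r = 1.157 and rejection of 0.005 (205 replicates). Both directions therefore appear at the planned sample size.

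**The case against.** The strongest reply is that the rule will probably never be used. The primary model has about 612 subjects and six visits. In idealised simulations with normal data and 30% monotone dropout, UN fitted by Fisher scoring converged in 400 of 400 trials at 204 per arm, and again at 40 and at 20 per arm. That was not PROC MIXED and not real PANSS data, but it gives no reason to expect failure. This stands: the error rates above apply only after a UN failure, and they are not the error rates of the trial.

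The order and selection rule are also fixed in advance, and the table shells require the footnote to name the structure actually used. The choice therefore leaves no room for discretion. That stands too, but a pre-specified rule that contradicts its stated principle is still worth correcting.

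A reader might infer that non-convergence is more likely in the placebo-based imputation analyses. The SAP does not support this: Appendix 3 produces complete datasets before the MMRM is fitted, which should make UN no harder to fit. Subgroup models use smaller samples, but they lie outside the multiplicity procedure and their shell reports no p-values.

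A reader might also assume that FA0(6) would converge wherever UN fails. That has not been shown. It can settle on a singular boundary solution.

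**Conclusion.** The ordering error is certain and follows from the SAP text alone: FA0(6) has 21 parameters and sits behind structures with 11, 7 and 7. If UN fails, the primary and CGI-S tests move to a Toeplitz restriction while an equivalent unrestricted form is untried.

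The size of the harm is conditional and rests on assumed SDs, correlations and dropout. Under those assumptions the Week 6 SE is about 5-15% too small with rising adjacent correlations, about 5-20% too large with falling ones, and correct if the structure is truly Toeplitz. One direction raises the type I error and the other costs power.

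A stronger reading, that the rule inflates the type I error of the primary analysis, is not supported. The SAP does not allow the chance of a UN failure to be estimated, and the direction of the SE error is unknown. This is a modest correction worth making, not a flaw in the planned primary model.

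**What to change.** In Section 15.1.3, make FA0(q) the first alternative after UN, followed by TOEPH, ARH(1), CSH, TOEP, AR(1) and CS. Define q as the number of post-baseline visits at which the endpoint is measured: 6 for PANSS and CGI-S, 3 for MSQ (Weeks 2, 4 and 6). Add that an FA0 fit is accepted only after the estimated matrix has been checked for singularity, and that the next structure is tried if it is singular.

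The cost is one list entry moved and one or two sentences added. Nothing changes if UN converges. The small downside is the possible boundary solution, which the check addresses.

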#### 15.1.4. SENSITIVITY ANALYSIS OF PRIMARY EFFICACY VARIABLE

The following three patterns will be considered to separate informative (treatment failures) versus noninformative cases based on the reason(s) of discontinuation when imputation of missing values performed for subjects discontinued early:

**Pattern 1**: Discontinuation for any of the reasons: An adverse event, death, non-compliance, lack of efficacy, subject required treatment with a prohibited medication, pregnancy, physician decision, study terminated by investigator, study terminated by sponsor, subject withdrew consent, or other is informative;

**Pattern 2**: Discontinuation due to lack of efficacy, adverse event, or death is informative and discontinuations due to all other reasons are non-informative;

**Pattern 3**: Discontinuation due to lack of efficacy is informative and discontinuations due to all other reasons are non-informative.

The following sensitivity analyses will be performed for the primary efficacy variable:

**Scenario #1**: A pattern-mixture model (PMM) approach. Sensitivity analysis will consider a Missing Not At Random (MNAR) mechanism for the missing data, where it will be assumed that subjects who discontinue early from the HP-3070 treatment will follow the trajectory of outcomes similar to the one in the placebo arm after discontinuation of the HP-3070 treatment, taking into account observed values prior to discontinuation (Little and Yau, 1996; Ratitch et al., 2013). Subjects discontinuing early from the placebo arm will be assumed to have unobserved outcomes similar to placebo subjects who remain on placebo treatment. The assumption that efficacy profiles of dropouts after discontinuation of active treatment are similar to those of placebo subjects provides an estimate of efficacy attributable to the active treatment if received through the time point of interest, while limiting efficacy after early discontinuation to that of the placebo and trial effect. A pattern-mixture model approach using a placebo-based multiple imputation will be used for this analysis.

Intermittent missing data will be multiply imputed using the MAR assumption within each treatment arm. Monotone missing data (data missing after an early discontinuation) for all subjects (from placebo and HP-3070 treatment arms) will be multiply imputed using a placebo-based imputation model. The steps to implement this sensitivity analysis are detailed in Appendix 3.

PMM analysis may also be performed according to patterns 2 and 3. For these analyses, only the discontinuation reasons considered as informative will be imputed using the placebo-based imputation model; discontinuations for non-informative reasons will be multiply imputed using the MAR assumption within each treatment arm. PMM analyses for pattern 2 and/or pattern 3 may only be performed if dropout is considered high.

**Scenario #2**: A continuous responder analysis based on improvement from baseline in PANSS total score will also be performed as described in Section 15.3.1.9.

Scenario #3: Time-to-failure analysis will combine two types of missing data (missing at random and missing not at random). Time-to-failure analysis will be performed treating informative missing data as failures following pattern 1, 2, and 3, and using censoring rules for non-informative cases. Time to failure will be calculated from the first PANSS score after baseline that is <20% improvement from baseline if there is never an improvement in PANSS score >=20% during the study or from the first PANSS score that is <20% improvement from baseline after a timepoint with >=20% improvement.

Document:	\\quintiles.net\Enterprise\Apps\sasdata\SASb\SAS\Noven\HP-			
	3070\XWA17541\Biostatistics\Documentation\SAP\Final 6\Noven HP-3070-GL-04 SAP text Final			
	6_18Jan2018.docx			
Author:	[name]	Version Number:	Final 6	
		Version Date:	18Jan2018	
Template No:	CS TP BS016 – Revision 3	Reference: C	CS WI BS005	

Effective Date: 01May2012

Copyright © 2012 Quintiles Transnational Corp. All rights reserved.

Noven Pharmaceuticals, Inc. STATISTICAL ANALYSIS PLAN: PROTOCOL HP-3070-GL-04 Page 29 of 50

**Scenario #4**: Analysis of Covariance (ANCOVA) on rank-transformed data at Week 6, adjusted for baseline and country, will be also performed as sensitivity analysis.

In order to perform an ANCOVA on rank-transformed data, changes from Baseline to Week 6 in the PANSS total score will be transformed to ranks as described in Appendix 4. Before performing the rank transformation, subjects with missing data at Week 6 will be imputed with a change from baseline equal to the worst (largest) change from baseline in observed data plus 1 for informative cases following pattern 1, so that these subjects would have the worst (highest) rank after the transformation. (It should be noted that with an assignment of the highest rank to subjects with missing data, the rank-based ANCOVA, contrary to the primary analysis, does not assume a MAR mechanism, but rather implies the worst outcome for all early discontinued subjects regardless of treatment arm). The details of the rank-based ANCOVA are described in Appendix 4.

Sensitivity analysis to investigate impact of outliers on primary efficacy: To investigate the impact of outliers on the primary efficacy analysis, a sensitivity analysis will be performed by including outliers.

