## 5.3. FULL ANALYSIS SET

Full Analysis Set (FAS) includes all randomized subjects who have had at least 1 patch of double-blind study medication applied and who have a Baseline PANSS total score and at least 1 post-Baseline assessment of the primary efficacy measure (PANSS total score). The FAS will be used as the primary set for analysis of efficacy endpoints based on randomized treatment assignment.

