#### 15.1.3. PRIMARY ANALYSIS OF PRIMARY EFFICACY VARIABLE

The primary efficacy analysis will be performed for the Full Analysis Set.

The estimand in the primary analysis for efficacy for each dose is the difference between treatments groups (HP-3070 dose group vs. placebo) in the change from Baseline to Week 6 in PANSS total score in all subjects as randomized, under the assumption that all randomized patients remain on their randomized treatment throughout the trial. PANSS scores obtained 24 hours after removal of the double-blind study medication on Day 42 or PANSS scores obtained more than 24 hours after discontinuation of double-blind study medication and the subject switched to an approved antipsychotic treatment will be excluded as outliers. Outliers will be defined *a priori* as (i) PANSS total scores obtained more than 24 hours after removal of double-blind study medication on Day 42; or (ii) PANSS total scores obtained more than 24 hours after discontinuation of double-blind study medication and the subject switched to an approved antipsychotic treatment. Non-compliance/non-adherence to study treatment may lead to poor outcomes and introduce variability. The terminal half-life of asenapine from Saphris/Sycrest is 24 hours and the mean half-life of asenapine from HP-3070 patch ranged from 29.7 hours to 31.3 hours for all the application sites.

Considerable efforts will be made during the study conduct to prevent outliers. For example: site personnel will be instructed to not issue a day pass to patients on Day 41 (last day of double-blind patch application) and patients will be allowed to leave the clinic only after all Day 42 (Week 6) assessments are complete. Subjects without PANSS total score at Week 6 will be modeled as similar to those with data conditional on observed response history and covariates. All discontinued subjects will be assessed with PANSS total score at the time of treatment discontinuation.

The primary efficacy variable, change from Baseline to Week 6 in the PANSS total score for each of the 3 treatment arms, will be analyzed using an MMRM analysis. The MMRM model will include change from Baseline

Document:	\\quintiles.net\Enterprise\Apps\sasdata\SASb\SAS\Noven\HP- 3070\XWA17541\Biostatistics\Documentation\SAP\Final 6\Noven HP-3070-GL-04 SAP text Final		
Author:	6_18Jan2018.docx [name]	Version Number:	Final 6
		Version Date:	18Jan2018
Template No: CS_TP_BS016 – Revision 3		Reference:	CS_WI_BS005

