### Table 14.1.1 Analysis Sets

	Statistic	HP-3070 18.0 mg	HP-3070 9.0 mg	Placebo	Overall
Number of Subjects Screened in Run-in	Ν	XXX	XXX	XXX	XXX
Number of Subjects Randomized in Double-blind	Ν	xxx	xxx	XXX	XXX
Number of Subjects in the ITT Analysis Set	N	XXX	XXX	XXX	XXX
Reasons for Exclusion from the ITT Analysis Set:	n (%)	xxx (xx.x)	xxx (xx.x)	xxx (xx.x)	xxx (xx.x)
Not Consented	n (%)	XXX (XX.X)	xxx (xx.x)	xxx (xx.x)	xxx (xx.x)
Not Randomized	n (%)	XXX (XX.X)	xxx (xx.x)	xxx (xx.x)	xxx (xx.x)
Protocol Deviation	n (%)	xxx (xx.x)	xxx (xx.x)	xxx (xx.x)	xxx (xx.x)
Number of Subjects in the Full Analysis Set	n (%)	xxx (xx.x)	xxx (xx.x)	xxx (xx.x)	xxx (xx.x)
Reasons for Exclusion from the Full Analysis Set:	n (%)	xxx (xx.x)	xxx (xx.x)	xxx (xx.x)	xxx (xx.x)
No Double-Blind Study Medication Applied	n (%)	xxx (xx.x)	xxx (xx.x)	xxx (xx.x)	xxx (xx.x)
No Baseline Assessment of PANSS Total Score	n (%)	xxx (xx.x)	xxx (xx.x)	xxx (xx.x)	xxx (xx.x)
No Post-Baseline Assessment of PANSS Total Score	n (%)	xxx (xx.x)	xxx (xx.x)	xxx (xx.x)	xxx (xx.x)

Note: ITT = Intent-to-treat, PK = Pharmacokinetic, IVRS = Interactive Voice Activated Response System, IWRS = Interactive Webbased Response System.

Note: The all subjects screened set contains all subjects who provided informed consent for this study. This analysis set and the reasons for screening/run-in failure are based on data collected in the IVRS/IWRS. Some subjects in this analysis set do not have data recorded in the eCRF.

Note: The ITT analysis set includes all consented and randomized subjects.

Note: The Full analysis set includes all randomized subjects who have at least one patch of double-blind study medication applied, who have a baseline PANSS total score, and who have at least one post-baseline assessment of the PANSS total score.

Note: The Safety analysis set includes all subjects who have had at least one patch of double-blind study medication applied and who have at least one post-dose safety measurement during the double-blind treatment period.

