### Table 14.2.1.2.1.1 Treatment Comparison of Change from Baseline in PANSS Total Score at Week 6 – Pattern-Mixture Model Full Analysis Set

This table will be similar to 14.2.1.1.2.

Footnotes will be:

Note: PANSS = Positive and Negative Syndrome Scale, LSM = Least Squares Mean, SE = Standard Error, CI = Confidence Interval, N = number of subjects in the full analysis set by treatment group.

Note: The PANSS total score is the sum of all 30 items. Higher values represent greater severity of illness. If one or more items are missing at a given assessment, the total score is set to missing.

Note: Baseline is defined as the last non-missing measurement taken prior to first dose of double-blind study medication.

Note: A pattern-mixture model approach using a placebo-based multiple imputation has been used for this analysis.

Note: Imputed datasets are analyzed with the mixed linear repeated measures model including treatment, country, visit, treatment by visit interaction, and baseline value as covariates, and subject as random effect. The correlation of repeated measures within a subject is estimated with an unstructured covariance matrix. The Kenward-Rogers method is used to estimate the denominator degrees of freedom.

### Table 14.2.1.2.1.2 Treatment Comparison of Change from Baseline in PANSS Total Score at Week 6 – Pattern-Mixture Model for Dropout Pattern 2

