## Table 14.2.1.2.6 ANCOVA on Rank-Transformed PANSS Total Score Data at Week 6Full Analysis Set

	Т	'reatment Group		Treatment Group Comparison		
Statistic	HP-3070 18.0 mg (N=xxx)	HP-3070 9.0 mg (N=xxx)	Placebo (N=xxx)	HP-3070 18.0 mg (N=xxx)	HP-3070 9.0 mg (N=xxx)	
Rank-Transformed Change from Baseline to Week 6						
n	XX	XX	XX			
Mean	x.x	х.х	х.х			
SD	x.xx	x.xx	x.xx			
Median	X.X	x.x	х.х			
Min	х	х	х			
Max	х	х	х			
LSM estimate	х.х	х.х	х.х			
SE	x.xxx	x.xxx	x.xxx			
p-value				x.xxx	x.xxx	

Note: ANCOVA = Analysis of Covariance, PANSS = Positive and Negative Syndrome Scale, LSM = Least Squares Mean, SE = Standard Error, CI = Confidence Interval, N = number of subjects in the full analysis set by treatment group.

Note: The PANSS total score is the sum of all 30 items. Higher values represent greater severity of illness. If one or more items are missing at a given assessment, the total score is set to missing.

Note: Baseline is defined as the last non-missing measurement taken prior to first dose of double-blind study medication.

Note: The values of the change from baseline variable as well as baseline covariate are transformed to standardized ranks within each country, using fractional ranks and mean method for ties. Before performing the rank transformation, subjects with missing data at Week 6 due to discontinuation for any reason are imputed with a change from baseline equal to the largest change from baseline in observed data plus 1, so that these subjects have the highest rank after the transformation.

Note: Separate regression models are fit for each country using a regression model for change from baseline with baseline as predictor. Note: P-value is based on the Cochran-Mantel-Haenszel test, controlling for country. The hypothesis tested is the Row Mean Score Differ statistic, using the values of the residuals as scores.

Noven\HP-3070\XWA17541\Biostatistics\Production\Tables\xxxxx.sas ddmmmyyyy hh:mm

Author:

[name]

Version Number: Version Date: Draft 2 09Jan2017 Page **43** of **144** 

### Table 14.2.2.1 Treatment Comparison of Change from Baseline in CGI-S Score at Week 6

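### The worst-rank and placebo-based sensitivity analyses are described as covering all early discontinuations, but their tables use the FAS and omit randomised subjects with no post-baseline PANSS total

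*SAP*

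**What the plan says.** Section 15.1.3 defines the primary estimand "in all subjects as randomized, under the assumption that all randomized patients remain on their randomized treatment throughout the trial". Section 15.1.4, Scenario #4, gives the largest observed change plus 1 to subjects whose Week 6 value is missing under pattern 1, which lists every reason for discontinuation. It adds that the analysis "implies the worst outcome for all early discontinued subjects regardless of treatment arm". The footnote to Table 14.2.1.2.6 repeats the rule: "subjects with missing data at Week 6 due to discontinuation for any reason are imputed".

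Section 15.1.4 names no analysis set. Section 5.3 supplies the default: "The FAS will be used as the primary set for analysis of efficacy endpoints based on randomized treatment assignment". Besides a patch and a baseline PANSS, FAS membership requires "at least 1 post-Baseline assessment of the primary efficacy measure (PANSS total score". The shells follow this default. Scenario #4 is on the FAS for PANSS (Table 14.2.1.2.6) and CGI-S (Table 14.2.2.8). Scenario #1 is titled "Pattern-Mixture Model Full Analysis Set" for PANSS (Table 14.2.1.2.1.1), and likewise for CGI-S (Table 14.2.2.2). Scenario #3 (time to failure) is also on the FAS. Only Scenario #2, the continuous responder analysis, has an ITT version as well (Table and Figure 14.2.3.8).

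**The concern.** Scenarios #1 and #4 exist to show how far the result depends on what is assumed about subjects who leave. Both rules can handle a subject with no post-baseline data: the rank rule needs only the fact of discontinuation, and the placebo-based model can impute from baseline alone. Using the FAS puts a post-randomisation condition in front of rules that do not need it. A subject who leaves without any PANSS total is an early discontinuation under pattern 1, yet is dropped instead of being ranked worst. As programmed, the statement in Section 15.1.4 is untrue for these subjects. If their number differs between arms, the worst-rank comparison is no longer protected by randomisation at the point where it is meant to be most severe.

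**Working it through.** **Design figures.** Section 3.1 gives a difference of 7, SD 20, two-sided alpha 0.025 per comparison, and 204 evaluable subjects per arm for about 90% power. The normal approximation gives 203 per arm. The noncentral t gives 204, with power 0.900. The stated figure reproduces, and effect size 0.35 with n = 204 is used below.

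**Who is lost.** The shell for Table 14.1.1 has a row for FAS exclusion because of "No Post-Baseline Assessment of PANSS Total Score", so the SAP foresees the category. Sections 15.1.3 and 6.3 narrow it: a PANSS is planned at discontinuation, and early-termination data move to the next scheduled visit. What remains is subjects with neither a scheduled nor an early-termination total, including those whose only assessment has a missing item (Section 15.1.1 voids the total), plus any randomised subject who never received a patch.

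**Scenario #4, assumed rates.** Let w_a and w_p be the proportions ranked worst on active and placebo. The probability that an active subject ranks better than a placebo subject, with ties counted as half, is

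θ = (1 − w_a)(1 − w_p)·Φ(0.35/√2) + (1 − w_a)·w_p + 0.5·w_a·w_p, with Φ(0.35/√2) = 0.598.

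Assume 20% later dropout per arm. On the FAS, w = 0.20 in both arms: θ = 0.64 × 0.598 + 0.16 + 0.02 = 0.563. If a proportion e of an arm is excluded from the FAS, then on all randomised subjects w = 0.20(1 − e) + e. The approximate null standard error is √[(2n + 1)/(12n²)] = √[409/499,392] = 0.0286.

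| Excluded, active / placebo | w_a / w_p | θ, all randomised | Shift from 0.563 |
|---|---|---|---|
| 2% / 2% | 0.216 / 0.216 | 0.560 | −0.09 SE |
| 3% / 1% | 0.224 / 0.208 | 0.552 | −0.37 SE |
| 4% / 1% | 0.232 / 0.208 | 0.547 | −0.53 SE |
| 1% / 3% | 0.208 / 0.224 | 0.568 | +0.19 SE |

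For 3% / 1%: 0.776 × 0.792 × 0.598 + 0.776 × 0.208 + 0.5 × 0.224 × 0.208 = 0.552. At 204 per arm, 3% and 1% are about 6 and 2 subjects. The calculation ignores the baseline and country adjustment in Appendix 4.

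**Scenario #1, assumed rates.** Take the FAS difference as 7 and give excluded active subjects the placebo mean. The all-randomised difference is 7(1 − e): 6.86 at 2% and 6.65 at 5%, a change of 0.14 and 0.35 points.

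**Does the ITT MMRM close the gap?** No. Section 15.1.2 bars imputation, so a subject with no post-baseline change adds no record to the model in Table 14.2.1.1.2, whatever the table is called. The modification history of the shells also says the ITT analysis of the primary variable was removed, so that shell appears to be a leftover.

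**The case against.** The strongest case against has four parts.

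- Subjects are in-patients and a PANSS is planned at discontinuation. Someone who stops in the first days for tolerability should have an early-termination PANSS, enter the FAS, and receive the worst rank and placebo-based values. This stands. A reader might infer that the earliest failures as a group go unranked; the SAP does not support that, since only those whose planned assessment was not done or was incomplete, or who were never treated, are lost.
- The responder analyses already have ITT versions (Tables 14.2.3.6 and 14.2.3.8) in which missing counts as non-response, and Table 14.1.1 will show the exclusions by arm. This stands as partial mitigation, but it supplies neither a rank nor a placebo-based value.
- Holding the analysis set fixed and varying only the missing-data assumption is a legitimate sensitivity design. That is fair for a plan that says so. Here the text claims all early discontinuations.
- A reader might infer that the FAS makes the worst-case analysis look better than it should. The SAP gives no early-loss rate by arm, and the 1% / 3% row shows the FAS can be the less favourable set.

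**Conclusion.** The mismatch is real: Section 15.1.4 claims worst-outcome coverage of all early discontinuations, and the shells for Scenarios #1 and #4 leave out randomised subjects with no post-baseline PANSS total. The group should be small and its size is not stated. Under the assumed rates, balanced loss of 2% is negligible (0.09 SE). Unequal loss moves the rank probability by 0.37 SE (3% active, 1% placebo) or by 0.19 SE in the other direction (1%, 3%). Scenario #1 moves by at most 0.35 points for loss up to 5%. These figures rest on an effect size of 0.35, 204 per arm, 20% later dropout in each arm and assumed early-loss rates. The point concerns the stress tests only. It does not show the primary MMRM to be wrong, since the excluded subjects would add no record to it in any case.

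**What to change.** - **Scenario #4** (Tables 14.2.1.2.6 and 14.2.2.8): use all randomised subjects with a baseline score of the variable analysed, and give the worst rank to discontinued subjects with no post-baseline value.
- **Scenario #1** (Tables 14.2.1.2.1.1 and 14.2.2.2): for consistency use the same set, imputing all visits from the placebo model conditional on baseline. Appendix 3, Step 2 already conditions on baseline and earlier visits, so a baseline-only subject fits.
- **Scenario #3**: use the same set, counting these subjects as failures or censoring them according to the pattern rules.
- **Minimum alternative**: limit the sentence in Section 15.1.4 to early-discontinued FAS subjects, and point to the by-arm exclusion counts in Table 14.1.1.

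The ITT MMRM shell (Table 14.2.1.1.2) should not be cited as covering this gap.

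The cost is a change of analysis set in the titles, footnotes and programs concerned. Section 3.1 makes a baseline PANSS a condition of entering double-blind treatment, so no new PANSS data are needed. The SAP does not say the same of baseline CGI-S, hence the wording by variable analysed. The downside is that the sensitivity result may become slightly less favourable.
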